**7.7.2 Concomitant Medication:**

All concomitant medications will be summarized by treatment arm and standard listings will be produced.

**7.7.3 Laboratory Data and Physical examination:**

All the laboratory parameters and physical examination data will be summarized by treatment arm.

### 7.7.4 Pulmonary Arterial Hypertension Specific Treatments:

A frequency table for all the PAH specific therapies will be summarized by treatment arm.

Change in PAH therapies at each visit will be summarized by sub categories like Phosphodiesterase Inhibitors (PDE 5 Inhibitors) and Endothelin Receptor Antagonists (ERAs).

### 7.7.5 Diuretic Therapy:

A frequency table for diuretic therapy usage between the treatment arms will be presented.

### 7.7.6 Acute Vasoreactivity Testing (AVT)

Comparison of the positive responders vs. non responders and change in 6MWD at 18 weeks for active and placebo separately.

## 8.0 Interim Analysis

A formal interim analysis is planned in this study as follows:

1. Stop for futility (null hypothesis is accepted; there is no difference between iNO and Placebo).
2. Stop for efficacy (null hypothesis is rejected; there is difference between iNO and Placebo favoring iNO).
3. Sample size determination.
4. Stop in case of safety concerns. Safety concerns may be some imbalances in adverse events frequency which is not in favor of iNO. No formal statistical guideline is provided for this purpose, the sponsor relies on the medical expertise of DMC members.
5. Continue the trial with the planned sample size until next stage if point 1, 2 or 4 not apply.

The following two designs will define the interim analysis strategy:

- 1) Design 1: Groups Sequential Design (for efficacy part)
- 2) Design 2: Sample Size Re-estimation (SSR) (for futility and sample size re-estimation)

The interim analysis schedule planned as follows:

Schedule	Requirement
1 st	After 75 patients complete 18 Weeks of blinded treatment phase.
Final	After 150/188 (depending on CP and PP) patients complete 18 Weeks of blinded treatment phase.

Traditional group sequential design (GSD) alpha spending function  $\Gamma = -3$  ([Hwang, Shih, deCani, 1990](#)) is used to control the overall type 1 error at 0.025, 1-sided. The interim analysis rule ([Table 35](#)) is as follows.

**Table 35: Interim and Final Analysis Rules:**

Category	Rule
Efficacy	At interim analysis (after 75 patients), if the one-sided $p < 0.0046$ then the study will stop for efficacy (Wald Statistics)
Efficacy	At final analysis (after 150 patients or 188 patients depending on CP and PP), if the one-sided $p < 0.0229$ then the study will yield an efficacy conclusion. (based on CHW Statistics)
Futility	At interim analysis, if conditional power (CP) or predictive power (PP) $\leq 10\%$ then the study stops for futility.
Continue	At interim analysis, if $10\% < CP$ and $PP < 57.2\%$ then trial continues to 150 patients.
SSR	At interim analysis, if $57.2\% \leq CP$ or $PP < 80\%$ the sample size is increased to $N=188$ . The lower bound of the promising zone interval was calculated based on the minimum treatment effect needed to achieve 70% or higher CP.
Continue	At interim analysis, if $CP$ and $PP \geq 80\%$ and 1-sided $p > 0.0046$ , then the trial continues to $N = 150$ patients.

This is the "promising zone" sample size re-estimation (SSR) design of [Mehta & Pocock \(2011\)](#), which uses the [Cui, Hung, Wang \(1999\)](#) method of analysis to combine the test statistics for the separate analyses of the IA and post-IA parts of the trial, if the trial does not stop at IA.

The final analysis is via weighted Z statistic using equal weights for the IA and post IA test statistics. It requires  $p < 0.0229$  1-sided for statistical significance to control the overall type 1 error level at 0.025 1-sided with  $\gamma = -3$  error spending function ([Hwang, Shih, deCani 1990](#)).

## 9.0 Part II Analysis:

The primary objective of part II open label is incidence of AE and SAE. All the tables for Part I AE's will be replicated for Part II to assess long term safety and tolerability.

[figure not shown]
The secondary objective is to evaluate the change from baseline in 6MWD for subjects who change from Placebo to active therapy. Standard descriptive statistics will be presented. No formal statistical analysis is planned.

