- Pregnancy test
- Survival status
- All blinded drug cartridges from Part 1 of the study must be returned to the site or Sponsor.

Assessments Part 2

Part 2 Week 0 Visit: The following Assessments will be performed:

- Informed Consent
- Methemoglobin via pulse oximetry (O₂ flow rate)
- Drug Device Dispensation for Open Label treatment
 - If the subject continues to participate, at this visit the subject will be dispensed a 1 week supply of study drug. Additional supplies will be delivered directly to the subject's home every 4 weeks. The used cartridges must be returned and will be picked up from the subject's home when the new supplies are delivered.

- Pregnancy test (at the discretion of the investigator)
- Evaluation for symptomatic Rebound Hypertension while under medical supervision, after start of study drug and prior to sending the subject home as described in [section 11.1.15](#)

Part 2 Week 2 Visit is a Telephone Visit:

Study Staff will contact the subject via telephone call and the following assessments will be completed:

- Review of prior and concomitant medications
- Assessment of AE,SAEs, AESI

Part 2: Week 16, Week 32, and Week 52 Visits - the following assessments will be performed:

- Prior and concomitant medications
- WHO Functional Class
- Conduct 6 Minute Walk Test
- Borg Dyspnea Scale
- Laboratory – Hematology and Chemistry (Week 52 only)
- Pregnancy test (at the discretion of the Investigator)
- Vital Signs including HR, RR, BP and temperature. SpO₂ and methemoglobin (Week 52 only) via pulse oximetry (O₂ flow rate)
- Assess AEs, SAEs. AESIs
- Drug Device Dispensation (every 4 weeks via home delivery)
- Review Drug Device Usage
- Evaluation for symptomatic Rebound Hypertension while under medical supervision, after start of study drug and prior to sending the subject home as described in section 11.1.15

Part 2: Every 4 Month Visits: The following assessments will be performed:

- Prior and concomitant medications
- Assessment of AEs, SAEs, AESI
- Vital signs: BP and HR, SpO₂ and methemoglobin via pulse oximetry (annually)
- Review device usage with the subject
- Laboratory – Hematology and Chemistry will be conducted on a yearly basis (Pregnancy testing will be left to the discretion of the Investigator)
- Drug Device Dispensation (every 4 weeks via home delivery)

Part 2: End of Study (EOS) or Early Discontinuation- The following assessments will be performed:

- Prior and concomitant medications

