11.1.17. Adverse Events

Adverse events, including AESIs and serious AEs, will be assessed in Part 1 at Baseline, Weeks 2, 6, 10, 14, and 18, including and at any time of an early drug discontinuation before Week 18. If an AE, SAE or AESI occurs while the subject is at home, then either the subject, the subject's caregiver or family member, or other responsible person will contact the study coordinator or Investigator at the research site and that person will record, assess, and report the event as indicated. In Part 2 at Week 2, Week 16, Week 32, Week 52, every 4 months and Early Discontinuation/End of Study

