11.1.17.1. Adverse Events of Special Interest

AESIs will include all respiratory related AEs, epistaxis, syncope and rebound PH. All SAEs, and rebound PH will be adjudicated (see also [Section 15.7](#)).

At each visit, subjects should be queried on all AESIs. Respiratory AEs should be specifically sought out. Subjects should be comprehensively queried for, e.g., hospitalization for any reason, pulmonary infections, important increases in chronic pulmonary medications, dyspnea, cough, hypoxia, acute respiratory failure, bronchitis, epistaxis, syncope including pre-syncope and loss of consciousness (new onset, or if history of syncope, recurrent syncope events), signs and symptoms of rebound PH and any other respiratory related AEs. These queries are to be documented in the eCRF on a separate page dedicated to AESIs. The severity of all AEs (AESI and non-AESI), treatment given, hospitalization required, and duration in number of days should be recorded in the AE section of the eCRF.

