15.4.1. Collection of Adverse Events and Serious Adverse Events

Any AE occurring prior to signing the ICF should be considered medical history or a pre-existing condition, and will be collected on the Medical History eCRF. Findings at Screening from physical exam, baseline laboratory results, etc. should also be considered medical history or pre-existing condition and be recorded accordingly.

At each visit, the Investigator will determine whether any AE has occurred and if it is related to the investigational product. Subjects will also be instructed to contact the site to report any AE that occurs between study visits. For randomized subjects, AEs and SAEs will be collected from signing of the ICF through the EOS and entered on the AE section of the eCRF.

SAEs (including those related to investigational product complaints/deficiencies) occurring from signing of the ICF through the EOS will be reported to Bellerophon Pulse Technologies Drug and Device Safety Department or their designee within 24 hours of an Investigator becoming aware of the event, using the AE/SAE page in the eCRF.

As laboratory abnormalities may fall into the category of expedited reporting, the Investigator will review the clinical laboratory test results in a timely fashion. Only those results qualifying as AEs/SAEs will be recorded in the AE section of the eCRF.

Adverse events will be coded according to the most current version of MedDRA in use. All medical device deficiencies associated with a SAE will be coded and reported as required.

For consented subjects who are screen failures prior to randomization, AEs will not be collected after the subject fails to qualify for randomization.

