### 7.7.1 Adverse Events:

The adverse events will be coded in accordance with Bellerophon standard procedures. The incidence of Treatment emerged adverse events (the percentage of subjects having experienced at least one AE) during a defined study period will be determined. Only adverse events with a start date on or after the date of randomization will be taken into account.

The following categories of adverse events will be compared between two treatment groups using Fisher's exact test.

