**From Date of Randomization through End of double blind period (Week 18):**

- All events through end of blinded period (week 18),
- All events at Body System Organ class level through end of blinded period (week 18),
- All events at preferred term level through end of blinded period (week 18).

Comparison between groups of the incidence of serious adverse and the incidence of death (if any) will be done by Fisher's exact for the treatment period and the entire study through post treatment follow-up.

All AEs will be listed for each patient and summarized by formula groups according to the System Organ Class (SOC) and Preferred Term (PT) assigned to the event using MedDRA. All the summary tables will be presented from randomization through end of treatment for blinded phase of study and from randomization through end of follow-up period.

The following will be summarized for subjects in safety analysis set:

- Adverse events in any category - patient level
- Adverse events in any category - episode level
- Adverse events by system organ class and Preferred Term
- Adverse events by SOC and PT presented by maximum reported severity
- Adverse events related to study product, presented by SOC and PT
- Adverse events leading to withdrawal of study product, presented by PT, arranged by SOC
- Adverse events causality related to study product, presented by SOC and PT
- Adverse events leading to study product interruption, presented by PT, arranged by SOC
- Adverse events leading to dose reduction of study product, presented by PT, arranged by SOC
- Adverse events leading to increase in dose of study product, presented by PT, arranged by SOC
- Adverse events leading to discontinuation of study product, presented by PT, arranged by SOC
- Key information for serious adverse events
- Serious adverse events causality related to study product, presented by SOC and PT
- Serious adverse events leading to study product interruption, presented by PT, arranged by SOC
- AE's on special interest

AE/SAE data collected at screening will be presented for all enrolled patients separately.

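### Part 2 AE and SAE incidence is a crude percentage over open-ended, unequal follow-up, so it is confounded with duration and, for non-serious events, with sparser contacts

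*SAP*

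**What the plan says.** SAP 7.7.1 defines AE incidence as "the percentage of subjects having experienced at least one AE". It adds that the "summary tables will be presented from randomization through end of treatment for blinded phase of study and from randomization through end of follow-up period". It also plans Fisher's exact tests of SAEs and deaths for the treatment period and for the whole study. One further table counts events at episode level, again without person-time.

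SAP 9.0 carries this over to the extension: "All the tables for Part I AE's will be replicated for Part II to assess long term safety and tolerability". Protocol 7.2 and SAP 4.4 make AE and SAE incidence the Part 2 primary endpoint. Neither document plans an exposure-adjusted rate or a table by time interval.

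Part 1 lasts at most 18 weeks (SAP 5.1). Part 2 continues until marketing approval or a sponsor decision to stop (Protocol Synopsis; Protocol 8.1), and all subjects in it receive iNO.

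On collection, Protocol 11.1.17 reads "Adverse events, including AESIs and serious AEs, will be assessed in Part 1 at Baseline, Weeks 2, 6, 10, 14, and 18", and then "In Part 2 at Week 2, Week 16, Week 32, Week 52, every 4 months and Early Discontinuation/End of Study". For the Part 2 Week 2 contact, Protocol 11 says "Study Staff will contact the subject via telephone call and the following assessments will be completed". Protocol 11.1.17.1 ties prompted questioning to visits: "At each visit, subjects should be queried on all AESIs". Between visits, Protocol 15.4.1 provides that "Subjects will also be instructed to contact the site to report any AE that occurs between study visits", and SAEs go to the sponsor within 24 hours of the investigator becoming aware of them.

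**The concern.** A percentage with at least one event depends on how long each subject is watched. Part 1 has a short and nearly common follow-up, so the measure is serviceable there. Part 2 does not. The Synopsis expects Part 1 enrolment from June 2016 to January 2018, so a single stop date would by itself spread Part 2 exposure over about 19 months.

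A second influence works the other way. Staff ask about AEs far less often in Part 2, and the resource-use forms, which investigators review for possible AEs, are recorded only in Part 1 (Protocol 11.1.24). Non-serious events that resolve between visits may be missed more often.

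At stake is the reading of long-term safety. Identical Part 1 and Part 2 tables invite a side-by-side reading, in which longer follow-up can look like rising risk and sparser questioning like falling risk. Respiratory events are where this matters most: SAP 2.0 reports 9 SAEs at 75 mcg/kg IBW/hr against 4 in each other Phase 2 group and describes the excess AEs as respiratory (Protocol 5.1 calls the SAEs balanced).

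**Working it through.** The documents give no AE rate and no safety sample size, so there is no planned safety figure to reproduce. The schedule can be checked. SAP Table 18 target days should equal 126 + 7 × Part 2 week: Week 2 gives 140, Week 16 gives 238 and Week 32 gives 350, all as printed. (Table 18 has no Week 52 row; Table 21 does.)

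**Contact gaps** (Protocol 11.1.17)

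| Period | Gaps, weeks | Mean gap | Contacts per 52 weeks |
|---|---|---|---|
| Part 1 | 2, 4, 4, 4, 4 | 18/5 = 3.6 | 5/18 × 52 = 14.4 |
| Part 2, year 1 | 2 (telephone), 14, 16, 20 | 52/4 = 13.0 | 4 |
| Part 2, later | 52/3 = 17.3 | 17.3 | 3 |

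**Duration alone.** Assume a constant hazard and full capture. With p the 18-week risk, P(at least one event by week T) = 1 − (1 − p)^(T/18). For p = 20% and T = 52: 1 − 0.80^2.889 = 47.5%. The values of p are assumptions spanning a range.

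| Assumed 18-week risk | 52 weeks | 104 weeks | 18 + 52 = 70 weeks | First events per 100 patient-years |
|---|---|---|---|---|
| 5% | 13.8% | 25.6% | 18.1% | 14.8 |
| 20% | 47.5% | 72.5% | 58.0% | 64.5 |
| 40% | 77.1% | 94.8% | 86.3% | 147.6 |

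The last column is −ln(1 − p)/18 × 52 × 100. It is the same at every follow-up length, so a person-time rate removes the duration effect.

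**Schedule alone.** Assume an event not reported spontaneously is recalled at the next contact with half-life h weeks, and that a share s is reported spontaneously. With k = ln 2/h, the captured share over a gap L is c(L) = (1 − e^(−kL))/(kL). Weighting by gap length gives a schedule average C, and total capture is s + (1 − s)C.

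| h, weeks | C, Part 1 | C, Part 2 year 1 | Ratio, s = 0 | Ratio, s = 0.8 |
|---|---|---|---|---|
| 4 | 0.735 | 0.345 | 0.47 | 0.92 |
| 8 | 0.853 | 0.540 | 0.63 | 0.94 |
| 16 | 0.923 | 0.718 | 0.78 | 0.96 |

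With no change in true risk, the reported Part 2 rate would be 0.47 to 0.96 of the Part 1 rate. Exposure adjustment does not remove this.

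**Both together**, 18-week risk 20%, unchanged hazard, over the same ranges of h and s: Part 1 would report 15.1% to 19.7%, the first 16 weeks of Part 2 8.3% to 17.3%, and the first 52 weeks of Part 2 20.0% to 45.6%. The same constant risk can look lower or higher than in Part 1, depending on the window read.

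**The case against.** The strongest reply is that Part 2 is an uncontrolled extension meant to describe long-term safety, and that no Part 1 versus Part 2 test is planned. Both are true. The difficulty arises when the tables are read side by side or accumulated. But a description of long-term incidence that does not account for time at risk is weak on its own terms.

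Several stronger readings are tempting and are not supported:

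- A reader might infer that incidence tracks schedule and duration and not the drug. It still depends on the drug; the other influences are mixed in. AE contacts are scheduled alike for both arms in Part 1, and alike for former placebo and former iNO subjects in Part 2, so schedule alone does not bias those contrasts.
- A reader might infer a large loss of events in Part 2. Spontaneous reporting applies throughout (Protocol 15 and 15.4.1), an AE still present at a visit can be found there, and SAEs have the 24-hour rule. The ratio could be close to 1.
- A reader might infer contacts only every 16 to 20 weeks. The first Part 2 gaps are 2 and 14 weeks. Nor is every AESI looked for less: supervised rebound PH evaluations fall at Weeks 0 and 2 in Part 1 and at Weeks 0, 16, 32 and 52 in Part 2 (Protocol 11.1.15).
- A reader might take the cumulative tables as certainly spanning both parts. The SAP does not define the end of follow-up, and the sentence stands under a heading limited to the double-blind period. The reading is likely, not explicit.
- A reader might treat non-serious AEs leading to discontinuation as independent of visits. Nothing in the documents says so.

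**Conclusion.** The point holds for duration. A crude percentage over open-ended, unequal follow-up cannot separate longer exposure from higher risk: 20% at 18 weeks becomes about 48% at 52 weeks under an unchanged hazard. The direction is certain; the size rests on the assumed 18-week risk and the constant hazard.

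For non-serious AEs there is also possible under-ascertainment in Part 2. Its cause is documented, but its size is not: the 0.47 to 0.96 range rests on assumed recall and spontaneous-reporting values. SAEs are much less exposed to it.

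If the whole-study Fisher tests extend into Part 2, events on open-label iNO in former placebo subjects could count against placebo. The SAP does not say how such subjects are classed.

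This is worth correcting. It bears on the Part 2 primary endpoint and on any safety table past Week 18, and touches no efficacy conclusion.

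**What to change.** In SAP 7.7.1 and 9.0:

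1. Make the main Part 2 AE and SAE summary, and any table or comparison running past Week 18, an exposure-adjusted first-event rate: subjects with a first event per 100 patient-years at risk, with a 95% CI.
2. Present it by randomised arm and interval (Part 1; Part 2 months 0–4, 4–8, 8–12 and after 12), so that events on open-label iNO in former placebo subjects are shown separately. State whether subjects re-enter the risk set at the start of each interval.
3. Keep crude percentages as secondary, and define the end of the follow-up period.
4. Rest statements about change over time on SAEs and deaths. Footnote all non-serious AEs, including prompted AESIs, as not directly comparable between parts because contact frequency differs. This is needed because step 1 does not correct for sparser contacts, and a rate shown without it could suggest falling risk.

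The cost is SAP wording and extra tables from dates already collected, with no change to visits or treatment. The downsides are more output and the assumption of a roughly constant hazard within each interval.

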## 10.0 Statistical Software

SAS 9.4 or above and EAST 6.4 will be used for statistical analysis of the study.

## 11.0 Changes of analysis from Protocol

Changes	Reason

